## 7. Payment Procedures & Handling

All the THP funds are deposited into the MUHAS account and controlled by the MUHAS procurement officer. THP has a unique code that they will use to request funds from the MUHAS procurement officer.

- a. During the trial, **Project Coordinator** reviews the students' schedule of payments and the amount they will receive for participating in the study and send a request to the procurement officer.
- b. The procurement officer will procure the fund that is required for the task for the said period of time, e.g., a week.
- c. **Project Accountant**, a person in charge of payments, under **Project Coordinator's** guidance, will request a daily amount based on the number of participants for each day.
- d. Each morning, **Project Accountant** will collect student registration forms from Project Coordinator to the MUHAS procurement officer.
- e. **Project Accountant** will procure the funds from the MUHAS procurement officer each day and maintain them in a locked cabinet/lockbox. On the day of the study, he will hand students or standardize patients (SPs) the payment for completing the baseline assessment or seminar. The student/SPs sign that they have received payment. Every other day the original signatures from students will be handed over to the MUHAS procurement officer for records. **Project Accountant** will maintain a copy of the payments on file in the THP study office. The procurement officer will not release the fund for the next day without receiving the signatures from the previous day.
- f. **Seminar day:** We expect each student to be present in the seminars for 7 hours to be compensated. If a student attended less than 5 hours under any circumstances, he/she would not

be paid for that day. Project Coordinator and the team will evaluate each situation and make a decision about the students' absences.

## H. Seminar Preparation and Procedure

### 1. Prior to the Seminar

- a. **3-month Seminar Planning Meeting.** In June, **Project Coordinator** will hold a planning implementation meeting with all the trainers at the seminar. Using the proposed timetable (or schedule) from the Aim 2 subcommittee, the team will: (a) confirm the faculty member in charge of leading each section, including the faculty member in charge of each small group. (b) In case of illness, the meeting will also identify a backup faculty member to teach each segment. It is the responsibility of the backup member to be familiar with the material and ready to teach it if necessary. (c) The team will identify any difficulties they anticipate in running the training for 204 students, and brainstorm ways of solving these. Specifically, they will look at the time needed to feed people, answer questions, have breaks where 200 participants may need to use the restroom, and other logistical questions.  
(d) The team will also address the additional monitoring tasks involved in the training. These include (i) someone to take the temperature of each staff and participant when they arrive each day, (ii) someone monitoring the door of lecture Theater 4 to ensure only participants attend, and during the seminar to monitor and document any participant who arrives late, needs to leave early, and/or has questions about the evaluation being conducted, (iii) someone to help any students who is uncomfortable or upset by the material or who become ill during the training; (iv) a process monitor to conduct the fidelity check each day, and (v) someone to answer questions about payments. (vi) To keep on time, the team may want to appoint a time-keeper who can monitor time and cue the presenter when they are close to time.
- b. **Documents and handouts.** **Project Coordinator** is responsible to ensure that all the participant handouts are prepared well ahead of time. Given we are planning on 206 participants and 6 faculty, we will likely need 210-215 copies of any materials. **Project Coordinator** will create a list of all seminar materials needed. These may include:
  - i. 215 Short handbook and 250 pens, sufficient for each student to write notes
  - ii. 6 copies of the schedule (one for each leader and/or staff).
  - iii. copies of any written quizzes
  - iv. a question and answer box for any question's students may want to ask anonymously;
  - v. cards so that students can place questions in the question box
  - vi. 215 electronic reprints of the paper: Rosser et al. (2020) legal and Ethical Considerations in the Delivery of Sexual Health Care in Tanzania, African Journal of Health, Nursing and Midwifery, 3(7): 84-102. (This should be sent out to students the day before they are expected to discuss the cases in the ethics session).
  - vii. Other materials as identified by the faculty.
  - viii. Signs which seats are allocated to students to sit on and which to avoid
  - ix. Room signs for the “boot camp” day where students divide into three groups.

- x. Sign in and sign-out sheets for participants.
- xi. Two copies of the fidelity check form.
- xii. Signs for the timekeeper to hold out (e.g., 5min; 1min).
- xiii. 215 flyers thanking the students for attending the seminar and providing them with a cell phone and email on how to contact the study in case of sickness or other problems.
- c. ***Pre-meeting to Pilot Procedures for the Training and to Prepare the Room.*** 1-2 days before the training, the faculty should meet to finalize all tasks and to ensure all procedures are feasible. **Project Coordinator** should confirm when each person needs to be there, identify if any faculty may need to be absent for some reason and to assign who will monitor temperature, the door, be a referral for students, be the process monitor, and payments. At the meeting, the team should confirm when they will meet at the end of each day to debrief and to make any later minute changes to the following day. At this meeting **Project Coordinator** will determine who is responsible for preparing the room each day so it is ready when the first participant arrives.
- d. ***Feedback***
  - i. **Project Coordinator** asks each participant if they have any other questions or any feedback about their experience in the baseline assessment.
  - ii. For students who provide feedback, **Project Coordinator** logs this information for discussion at the team meeting.
  - iii. Whenever problems are identified and are immediate and easily fixed, **Project Coordinator** is authorized to modify study procedures to improve the student experience.

## 2. During the Seminar

**Objective:** The primary objectives during the seminar are to ensure:

- a. Participant and staff health and safety
- b. The training is professional and complete
- c. That participants have a good experience
- d. That at the end of the seminar, two things happen:
  - i. the post-seminar evaluation of the seminar is conducted
  - ii. Those participants are compensated

- a. ***Participant and staff health and safety.*** This is covered in the COVID protocol (see below).
- b. ***The training is professional and complete.*** **Project Coordinator** is responsible for monitoring the overall tone of the seminar, for making decisions when the seminar starts and ends each day, and whether the seminar should extend into Friday (in case power failure or other event affecting the students prevents them from receiving the full training).
- c. ***That participants have a good experience.*** All the team is responsible for ensuring that participants have a good experience. Based on other seminars, strategies each team member can do include:

- i. During the seminar show interest in the presentation. Avoid talking with other leaders in the back of the class or otherwise distracting participants from the presentation.
- ii. During breaks, ask participants how they are enjoying the seminar and express interest. Be available to answer questions that students may want to ask one-on-one.

- iii. During the debrief, bring any observations or student feedback to the attention of the team.
- iv. When presenting, keep to time, be prepared and know what is happening after your presentation so that transitions from one presenter to the next are seamless.

**d. Two things happen at the end of the seminar.**

**i. post-seminar survey:** Immediately after the training, students remain in the room to complete online post-test surveys that measure the change in knowledge and attitudes, as well as a process evaluation of the training (30 minutes).

**Back-up plan:** Should there be internet connection issues on the last day of training, then three study staff will be responsible persons for distributing and collecting paper copies of the surveys, and ensuring that all questions are filled out correctly. This will not be the case for online Qualtrics surveys since the survey will be programmed in a way that will minimize incomplete responses and data entry errors.

**ii. That participants are compensated**

Students in the training will be notified when they will receive a token of appreciation for their participation in the study after they have finished participating in the trial. The study coordinator **and Project Accountant** will be responsible for compensating students and making sure all participants sign the attendance and payment sheet. Each student will be responsible for signing a log showing the total compensation for study financial records and accounting (auditing) purposes. **Project Accountant** will be preparing a payment protocol and is responsible for handling and documenting participant payments.

Compensation will be prorated according to the number of days the student participated in the trial - Students will not receive financial compensation for days where they have unexcused absences. Each participant is responsible for attending each day of the trial. **Project Coordinator** is responsible for determining whether an absence is excused.

Students will be compensated for travel expenses, accommodation, and food each day during the trial.

**Compensating SP:** Each SP will be paid a daily stipend of 52 USD per day, for completing the post-seminar evaluation.

**3. Anticipated challenges and how to address them**

1. **If a student arrives late or leaves early, what happens?** If a situation like this happens then the supervisor (**Project Coordinator**) will discuss with the students if she wishes to continue or not. The supervisor will weigh the reasons provided and the time frame then he will make decisions.
  - a. **Project Coordinator** is the person responsible for deciding who can enter the study or not. We anticipate two types of non-attendance:
  - b. **Group non-attendance.** If because of weather or some other event a significant portion of the participants cannot attend, then **Project Coordinator** shall decide whether to delay the start of the seminar and/or change the timetable to facilitate everyone's attendance.
  - c. **Individual non-attendance:**

- i. If an individual notifies the study that s/he cannot attend, then if it is on or before Day 1 of the seminar, Project Coordinator shall replace this participant with one of the waitlist participants.
- ii. If an individual arrives within an hour of the seminar starting, study staff will record the time of arrival, the student's ID number, and any reason given for lateness, before admitting them. Similarly, if a participant needs to leave up to an hour early, study staff will record the time of departure, student's ID, and any reason given for the early departure.
- iii. If an individual is more than an hour late or needs to leave more than an hour early, or requests being absent from the training for more than an hour, this shall be referred to **Project Coordinator**. They will decide whether to let the participant continue and whether the participant receives compensation for that day. (Note: We prefer students to continue receiving the training and, in the study, wherever possible).

d. **Individual withdrawal from the Study.** This study is voluntary, therefore if anyone chooses to withdraw from the study, study staff will allow them to do so. Anyone notifying the study that intends to not attend the rest of the training shall be referred to **Project Coordinator**. **Project Coordinator** will review the intent of the participant and any reason why they will not be continuing in the training. Depending on the reason (e.g., sickness, family emergency, the decision to withdraw), he will thank them for informing the study of this decision, inform them that they will be compensated for the days attended but not days not attended, and will record the reason given why the participant dropped out of the study. Finally, **Project Coordinator** will ask if the participant is dropping out of the training only, or is wishing to drop out of the study. (NOTE: If a participant drops out of the training, they are still considered a participant and we prefer them to complete the post-seminar evaluation and the follow-up even if they missed part of the training).

2. **If a student misses a survey, what happens?** If a student is missing the baseline survey and/or the SP evaluation, he/she will not be allowed to participate in the training. Instead, his/her place will be given to one of the students on the waitlist.

#### 4. After the seminar

Two faculty (**Dr. X, Project Coordinator**) are identified resources for students following the seminar. At the end of the seminar, all participants are informed that if any student has follow-up questions, concerns or issues, they should contact either **Dr. X** or **Project Coordinator**. The role of **Project Coordinator** and **Dr. X** in this situation is to determine if this is a clinical issue or simply feedback on the seminar.

##### **If it is a clinical concern, Project Coordinator or Dr. X shall:**

- a. Assess and advise any student who reports difficulty following the seminar. For example, a student might wish to discuss some personal experience (e.g., history of assault, sexual difficulty). In this case, the faculty shall provide brief supportive counseling, and where appropriate, help the student to develop a plan to get more help if needed.
- b. For a student in difficulty, the faculty shall be a resource and will check in with the student.
- c. While protecting the student's confidentiality, **Dr. X** and **Project Coordinator** should log the details of the presenting concern and any action recommended or taken. Without compromising the student's confidentiality, any such concerns should be reported to Simon within 10 days of the event.

- d. As mandated reporters, should a student report themselves to be an immediate threat to themselves or others, the faculty member shall take whatever appropriate response, including if necessary breaking confidentiality, to preserve life.
- e. **The Principal Investigator (UMN)** is responsible for reporting all such incidents to the IRBs of each institution if it is deemed an adverse event or an unanticipated or new finding. He is also responsible for informing the Principal Investigator at MUHAS, the senior leadership team, and if appropriate, the NIH.

*If it is a not clinical concern, Project Coordinator, Dr. X, or any other team member shall:*

- a. Address the feedback from the student and provide any information as appropriate.
- b. Email **Project Coordinator** that a student has followed up with them about the training. The email should provide a brief note, “e.g., a student stopped me to say they found the training really helpful,” or “a student said they used the training in addressing a patient.”
- c. **Project Coordinator** is responsible for keeping a log of this feedback and for bringing them to the attention of the Principal Investigators and/or the senior leadership team, or the whole team, as appropriate.

## 5. Additional Resources

**Prof. Z** will create a list of educational materials/resources such as a website, scientific manuscripts, peer to peer learning as part of the seminar to get additional information. Provide references for all the information that they can look for online. This needs to be done by **mid-July**.

## 6. Study Quality control/intervention fidelity

Intervention fidelity will be monitored by two investigators (i.e., **Principal Investigator and Dr. X**) observing each seminar. In the time where **Dr. X** is delivering a lecture, **Researcher 2** will assist **Dr. X** to conduct a fidelity check. Monitors will note the start and end times of each session, monitor curriculum fidelity, note any unusual events, provide ongoing feedback to the two seminar leaders, and write up notes for a train-the-trainer manual.

### I. Data Management and Storage

#### 1. Data entry for hard copies for participants who complete paper surveys.

The project Coordinator (**Project Coordinator**), will be responsible to identify vendors who will conduct data entry after data collection. Data entry will be done at MUHAS, and later unidentified electronic data will be shared with the rest of the team. All data will be stored in the cloud on BOX.

#### 2. Data storage (Baseline survey, SP and learners Checklists, and consent forms)

**Researcher 2 and 3** will submit completed surveys each day to the project coordinator (**Project Coordinator**). **Project Coordinator** will be responsible for making sure that these surveys are locked and confidentiality is maintained. All pen and paper survey responses will be stored at the MUHAS ([name] office) in the locked cabinet. All databases will be stored on MUHAS ([name] office) servers behind password-protected files, and made available to researchers as a de-identified data set. A copy of all the data will also be stored on BOX per University of Minnesota policy. Personal comments to open-ended questions will be checked and, if necessary, redacted to preserve confidentiality. After data entry for both pilot and trial, the original survey will be returned to the locked cabinet at MUHAS and then stored until 3 years after the study ends.

#### 3. Storage of SP and Learner Zoom Records

**Project Coordinator** will be responsible for storing data for all the recorded zoom videos for SP data. All electronic data will be stored in the secured drive protected by passwords in multiple places (in the external drive and in the computer) to avoid data loss.

At the end of each session, the IT person will make sure each session's recorded videos/clips are saved before inviting another learner into the station. **Project Coordinator** will identify the vendor who will do data entry and share the anonymous data to U of M staff for analysis.

#### 4. **Video Data for RCT**

A 3,296 video clips (412 participants x 4 videos x 2 admins) will each be assigned a unique code number matched to a master database. All videos are uploaded into the database and stored at two sites in Tanzania. Video data will also be saved to the BOX cloud at the end of each day.

- a. Project Coordinator is the data manager for the videos which will be saved in password-protected files. Since the videos contain identifying information (faces), he will allow access to the videos on an as necessary basis.
- b. **Rating: Drs. Y and X** will oversee the rating of videos.
- c. Videos are randomized so raters are blind to participant condition assignment (intervention or control) and blind to whether the assessment is pretest or posttest.
- d. No videos are reviewed by the expert raters until all the videos have been completed.
- e. On the rating form, the rater begins the review by writing out the Student ID, the three-digit Case-SP number (as reported on the video), and their assigned rater ID.
- f. Once the raters have rated all the videos their ratings are sent to **analyst**. **Study analyst** has the key to the blind and so can identify for each student, which are the two baseline videos and which are the two follow-up videos.

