So, [name] is say, 09. When [name] is acting for Case Study B. the number is 509. But if [name] also works on Case study D, that would be 709.

- d. Treatment arm: [THIS INFORMATION IS DELIBERATELY NOT IN THE SOP SO THAT THE TEAM MEMBERS AT MUHAS EVALUATING THE SP VIDEOS REMAIN BLIND TO THE CODE. THE CODE IS TWO NUMBERS BETWEEN 20 AND 79 GENERATED BY METHODOLOGIST. SHE WILL SEND THESE NUMBERS TO PROJECT COORDINATOR WITH THE INSTRUCTION TO USE THEM WITH THE PARTICIPANTS AT BASELINE. AT FOLLOW-UP METHODOLOGIST WILL SEND ANOTHER SET OF NUMBERS, ALSO BETWEEN 20 AND 79 FOR USE ONLY AT FOLLOW-UP. METHODOLOGIST WILL RETAIN THE KEY TO INTERPRETING THESE DIFFERENT NUMBERS].
- e. Expert raters are assigned a number that mirrors the SPs, starting at 51-60
  - i. Expert Rater Case study A – 451-460 (one for each rater)
  - ii. Expert Rater Case study B – 551-560
  - iii. Expert Rater Case study C – 651-660
  - iv. Expert Rater Case study D – 751-760

So, **Researcher 2** is assigned a unique number, say, 55. When **Researcher 2** is evaluating Case Study B, she assigned each case 555. But if **Researcher 2** also evaluated Case Study C, she would use the number 655.

Examples:

So, the study number appearing on a survey may look like this:

671423 – 02 – 300 – 54

Student ID# – Midwifery student – follow-up survey – Intervention arm

451207 – 03 – 100 – 27

Student ID# – Nursing student – baseline survey – Control arm

671523 – 01 – 200 – 54

Student ID# – Med student – post-test survey – Intervention arm

So, the study number appearing on an SP rater form may look like this:

671523 – 01 – 401 – 54

Student ID# – Med student – Case Study A (John SP) – Intervention arm

671423 – 02 – 603 – 54

Student ID# – Midwifery student – Case Study C (Sara SP) – Intervention arm

451207 – 03 – 502 – 27

Student ID# – Nursing student – Case Study B (Mary SP) – Control arm

The number on the expert rating form will look like this

451207 – 03 – 502 – 27 – 553

Student ID# – Nurse – Case Study B (Mary SP) – Control arm – **Dr. X** rater

671423 – 02 – 402 – 54 – 455

Student ID# – Nurse – Case Study A (John SP) – Intervention arm – **Researcher 2** rater

671523 – 01 – 702 – 54 – 753

Student ID# – Nurse – Case Study D (John SP) – Intervention arm – **Dr. X** rater

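### The expert rating form, as described, carries identifiers that weaken the stated rater blind, although nothing in the documents shows that the blind was broken

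*Protocol*

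**What the plan says.** Protocol Section I.4 (Video Data for RCT), item c, sets the standard: "Videos are randomized so raters are blind to participant condition assignment (intervention or control) and blind to whether the assessment is pretest or posttest". Item d adds a safeguard: "No videos are reviewed by the expert raters until all the videos have been completed". Each clip "will each be assigned a unique code number matched to a master database".

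Item e then describes the form: "the rater begins the review by writing out the Student ID", followed by the Case-SP number and the rater's own ID. Section D defines the Student ID as the university-issued number, to be used on every study document and spoken at the start of each video.

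Section D also shows a longer identifier. Under the line "The number on the expert rating form will look like this" it gives three examples, each with five parts: Student ID, profession, Case-SP number, treatment arm and rater. The arm part is 27 (labelled control) or 54 (labelled intervention). The same section explains that the meaning of the code is withheld so that the people evaluating the videos stay blind to it. It adds "AT FOLLOW-UP METHODOLOGIST WILL SEND ANOTHER SET OF NUMBERS" and "METHODOLOGIST WILL RETAIN THE KEY TO INTERPRETING THESE DIFFERENT NUMBERS".

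Section I.5 makes expert-rated clinical skill one of three primary dependent variables. The SAP analyses follow-up minus baseline differences. It is silent on rating and blinding.

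**The concern.** Of the three primary variables, rated skill is the one that depends on a person's judgement of a student, so it relies most on the blind. Item c rests the blind on random ordering of the videos. Random ordering hides arm and visit only if nothing attached to the clip restores them.

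Two fields could do so. A real Student ID lets a rater see which clips belong to one student, and it is the same number that staff lists use. A code shared by everyone in an arm, and changed between visits, sorts clips into arm-by-visit groups whether or not the rater holds the key. If a rater came to know both arm and visit, leniency could enter the change score in one arm only.

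**Working it through.** **The plan's own figure.** Section I.4 gives 412 × 4 × 2 = 3,296 clips, and the product is right. Item f of the same section speaks of two baseline and two follow-up videos per student, which gives 412 × 2 × 2 = 1,648. The number matters here only for the cost of the fix.

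**Form fields side by side.**
- Section D: Student ID, profession, Case-SP number, arm code, rater.
- Section I.4, item e: Student ID, Case-SP number, rater.
- Difference: profession and arm code. The Student ID is in both.

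**What the Student ID reveals.** It does not name an arm. It links a student's clips to each other. It also matches the number in two places where arm is recorded or checked: the randomization master list (Section C.9, item e) and the list checked at the seminar door (Section D, item c). Section C.7 limits access: the participant list is locked away with two key-holders, and electronic files with names or IDs are password-protected. No section gives raters a list.

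**What the arm code would reveal if it is on the form.** The examples use one code per arm, and a new set is sent for follow-up. That makes 2 arms × 2 visits = 4 codes, one for each arm-by-visit group. A rater without the key sees four unlabelled groups. With the Student ID also present, the codes pair up, because each student's baseline code goes with one follow-up code. Knowing the arm of a single student then labels both codes of that arm, and knowing the visit of a single clip labels the visit for every clip with that code.

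**What does not reveal the visit.** Cases are counterbalanced: half the students do cases A and B at baseline and half do them at follow-up (Section G.4, item vii). The case number therefore carries no visit information.

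**Can a size be given?** Assume that a share s of ratings is made by raters who know the arm, that they identify the visit correctly with probability q, and that they add d SD of the change score to intervention clips they take to be follow-up. The shift in the mean change is

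s·d·q − s·d·(1 − q) = s·d·(2q − 1).

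At q = 0.5 this is zero for every s and d, and the false-positive rate stays at 5%.

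For other values, take the SAP's 396 students, assume 198 per arm, so SE = √(2/198) = 0.1005 SD, and use rate = P(|Z + shift/SE| > 1.96):
- s = 0.2, q = 0.6, d = 0.3: shift 0.2 × 0.3 × 0.2 = 0.012, rate 5.2%.
- s = 0.5, q = 0.75, d = 0.3: shift 0.5 × 0.3 × 0.5 = 0.075, rate 11.6%.
- Same ranges of s and q with d from 0.1 to 0.5: rate 5.0% to 23.8%.

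None of s, q or d has a source in the documents, and the number of students with usable videos is not given. The spread only shows that the answer is set by the inputs chosen.

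**The case against.** The case on the other side has real strength.

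- *Item e may not list every field, and Section D does not say that raters read the arm part.* True, so this is not proof of exposure. It is still unclear whether the form in the rater's hands carries the code, and that needs settling.
- *The code is masked, the methodologist keeps the key, and rating starts only when all videos are in.* These are genuine safeguards. Masking hides what a code means but not the grouping it creates.
- *Raters have no list, and access is restricted.* This stands, and it limits what the Student ID can reveal.
- *The ID protects against mix-ups.* This also stands. Section D relies on it for that purpose, so the check should be moved and not dropped.
- *Faces stay visible on the videos.* They do, so the fix cannot protect against a rater who recognises a student. But recognition covers only students the rater knows, while a shared code could extend one recognition to a whole arm.

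Three stronger readings are tempting and are not supported:

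- *Raters were drawn from seminar or randomization staff.* The role labels of the example raters in Section D also appear in Sections C.9 and H.6. The examples may be illustrative, the labels are placeholders, and Section G refers to a staff overview that is not in the text available. The absence of a visible rater-independence rule is therefore not evidence that none exists.
- *The spoken ID is a visit cue*, because the baseline steps (Section G.4) include it and the follow-up steps (Section N.4.d) do not. Section D asks for it on each video, Section N.4 asks that follow-up replicate baseline methods as far as possible, and Section N foresees a revision. This is wording to reconcile.
- *The test has an inflated error rate of some stated size.* Every such figure rests on assumed inputs.

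**Conclusion.** The point holds in a limited form. The Protocol promises raters blind to arm and visit, but the rating form it describes carries the real Student ID and, in one of two descriptions, a code that would group videos by arm and visit. That weakens the protection. A reader might infer that the blind failed or that the skills result is biased, but the documents show neither.

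The size of any bias cannot be estimated from the documents. It is zero in the change score if raters cannot tell the visit, assuming that leniency adds equally at both visits and that rated skill is analysed as a difference score. The second assumption needs saying because the SAP refers to a list of outcomes that is not in the text available. The point merits correction because the outcome is primary and a neutral clip code is already planned.

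**What to change.** - On expert rating forms, replace the Student ID and arm code with the unique clip code already assigned in Section I.4, plus the case/SP number and rater ID. Amend Section D and Section I.4, item e, so that they describe the same form.
- Keep the Student ID check for mislabelled clips with the data manager, at the time the clip code is assigned.
- Have the analyst merge student, arm and visit only after ratings are locked, which extends Section I.4, item f.
- Make the spoken-ID step the same at both visits, reconciling Sections G.4 and N.4.d with Section D.

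**Cost.** The wording changes are minor. The clip coding and linkage is a small task: at an assumed one minute per clip, 1,648/60 = 27.5 hours, or 3,296/60 = 54.9 hours on the Protocol's count. Raters would no longer cross-check the ID.

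**If rating is already complete**, as the SAP date of December 2023 makes possible, state which form was used and qualify the blinding statement accordingly.

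**Optional.** Separating raters from seminar and randomization roles, starting playback after the spoken ID (which otherwise remains audible), and a sensitivity analysis excluding some raters are all reasonable. What the documents show does not require them.
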